5.2 Study interventions

Physicians in the replication trial randomized to one of the 2 active intervention arms will receive one of several possible enhanced EHR decision support to guide care. The type and timing of an alert will vary based on the intervention are outlined below. The two specific EHR tools for the replication trial at MGB was determined based on the adaptive randomized trial results:

Arm	Alert type	Open encounter	Follow-up booster	Pre-commitment
1	Enhanced	X	X	
2	Enhanced	X		X
Usual care	None			

Arms 1 through 2 are enhanced EHR tools to encourage the deprescribing of the medications under study. Physicians randomized to usual care will receive no intervention.

The central component of Arms 1 through 2 will be an enhanced EHR alert (known as a Best Practice Advisory [BPA]). The enhanced BPA will appear on each provider's EHR screen and will contain several standard components. The BPA will:

1. give providers information about why the medication is dangerous for their patient using the behavioral science principle of salience to make this information as impactful as possible;
2. include a set of tips to help providers discuss medication discontinuation with their patients;
3. ask providers to select an acknowledgment reason if they decided not to discontinue the medication;

4. include a SmartSet order set that will allow providers to order a gradual dose taper for their patient, which limits risks of withdrawal symptoms for the patients for benzodiazepines and sedative hypnotics, order alternative medications, place a referral to a behavioral health specialist, provide instructions on how to make lifestyle modifications to improve patient symptoms, and add customizable patient instructions for how to gradually taper off benzodiazepines and sedative hypnotics, as applicable.

We will also test several other modifications to this enhanced BPA. In specific, as outlined in the table above, we will add in a boosting option in the enhanced BPA in Arm 1, which is a provider-directed option for a follow-up in-basket message sent 4 weeks after the BPA is triggered. Arm 2 will test the use of a two-staged pre-commitment BPA in which the providers are prompted to discuss risks of these high-risk medications and share a handout about the risks with their patients, at their own discretion.

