5.3 Measures to minimize bias: randomization and blinding

Providers will be randomized to treatment arms in equal proportions based on blocks. We will use provider-based cluster randomization to minimize the possibility of contamination in study interventions between practices and clinic staff. For the randomization, we will use stratified randomization based on clinic practice size and baseline rates of prescribing to reduce potential imbalances between the providers assigned to the treatment arms.

The providers will not be blinded to which arm they were assigned to, as blinding is the context of an intervention that is intended to motivate action will be infeasible. The study

analyst will generate and implement the randomization scheme, with oversight by the Principal Investigators. Investigators will be blinded to the treatment arms during interim and final analyses.

6. Study Assessments and Procedures

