Tertiary outcomes will include the extent to which medications are filled and consumed by patients, as measured within the subgroup of patients with claims data. In specific, these outcomes will be conducted among the large subgroup of patients funded by Medicare, including pharmacy claims via the secure MedRIC data enclave. In particular, we will measure the quantity of high-risk medication dispensed, defined by number of milligram equivalents of high-risk medications filled by patients, in follow-up, using pharmacy claims data. Other tertiary outcomes will include the occurrence of clinically-significant adverse drug events, including but not limited to, sedation or cognitive impairment, and all-cause hospitalizations and falls or fractures, measured in administrative claims data. These clinical outcomes will be evaluated using validated and CMS-driven ICD-10-CM diagnosis and procedure-based algorithms applied to these patients' medical and pharmacy administrative claims data. Because the sensitivity of clinical outcomes in EHR systems is known to be low (e.g., because patients may seek subsequent care at other healthcare systems), using routinely-collected data from insurers overcomes this limitation.²⁴ We will also evaluate implementation of the intervention using structured deidentified data from the EHR about use of the EHR system, which will help inform how to scale the interventions (see Data to be collected form).

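### Falls, sedation, cognitive impairment and other adverse drug events are taken from claims diagnoses with no stated care-setting limit, so office coding could differ between the alerted and usual-care arms; a pre-specified inpatient/emergency companion analysis would show whether it matters

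*Combined protocol and SAP*

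**What the plan says.** Section 6.2 lists the tertiary clinical outcomes as adverse drug events, including "sedation or cognitive impairment, and all-cause hospitalizations and falls or fractures, measured in administrative claims data". On how they are found, it says: "These clinical outcomes will be evaluated using validated and CMS-driven ICD-10-CM diagnosis and procedure-based algorithms". The algorithms are applied to patients' medical and pharmacy claims. No restriction by care setting, claim type or coding clinician is given. The reason offered for using claims is that EHR data miss events, for example when patients are treated in another system.

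Section 5.2 gives both active arms an enhanced alert whose first component is to "give providers information about why the medication is dangerous for their patient using the behavioral science principle of salience". Arm 1 adds "a provider-directed option for a follow-up in-basket message sent 4 weeks after the BPA is triggered". In Arm 2, "the providers are prompted to discuss risks of these high-risk medications and share a handout about the risks with their patients", at the provider's discretion. Usual care receives nothing.

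Section 5.3 states: "The providers will not be blinded to which arm they were assigned to". It also states: "Investigators will be blinded to the treatment arms during interim and final analyses".

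The objectives table in Section 2 places these outcomes in the tertiary/exploratory tier and regards them as consequences of the targeted drugs. Section 7.3.2 analyses them as binary outcomes with a log link, giving relative risks.

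**The concern.** The person who may enter the outcome diagnosis is also the randomised, unblinded unit, and the intervention draws that person's attention to the drug's dangers in the active arms only. A provider so prompted may ask about and record a fall or an episode of confusion that a usual-care colleague would leave uncoded. Blinding investigators at analysis does not touch this, because the diagnosis is already on the claim by then. Better overall capture through claims does not touch it either: the issue is capture that differs by arm, not low capture in general.

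The trial hypothesises fewer such events in the active arms. Extra coding there works against that hypothesis and could be misread as harm from deprescribing. The stakes are raised by Section 6.3, which plans no patient-directed prospective adverse event monitoring and relies on provider reports. The claims outcomes are therefore the main systematic comparison of patient harm between arms.

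**Working it through.** **1. Is there a plan figure to reproduce?** Not for these outcomes. Section 7.2's power figure (over 80% for a 10-point difference from 25%, intra-provider correlation 0.1) concerns the primary outcome. For adverse events, sufficient power is asserted without an event rate, effect size or number of patients.

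**2. Does the text block the mechanism?** Set side by side:
- Section 6.2: no setting or coder restriction is stated.
- Section 5.2: harm information goes to Arms 1 and 2 only.
- Section 5.3: providers are unblinded; investigator blinding covers analyses only.
- Sections 7.3.1 and 7.3.2: covariate adjustment, censoring weights and multiple imputation are offered. None corrects outcome capture that differs by arm.

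Nothing blocks it.

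**3. How large could it be?** The documents give no coding rates, so both inputs are assumptions.
- s = share of counted patients, under usual-care coding, who qualify only through a randomised provider's code. The outcome is binary per patient, so an extra code adds nothing for a patient already counted from another claim.
- u = relative change in the number of such patients in the active arms that is due to coding alone.

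Observed RR = true RR × [(1 − s) + s(1 + u)] = true RR × (1 + s × u), taking the true RR to be the same for both kinds of event.

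| s | u | 1 + s × u | true RR 1.00 reads | true RR 0.85 reads |
|---|---|---|---|---|
| 40% | 10% | 1.04 | 1.04 | 0.88 |
| 50% | 20% | 1.10 | 1.10 | 0.94 |
| 60% | 20% | 1.12 | 1.12 | 0.95 |
| 80% | 30% | 1.24 | 1.24 | 1.05 |
| 60% | −20% | 0.88 | 0.88 | 0.75 |

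The last row shows the opposite direction: less coding in the active arms would exaggerate a benefit.

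Full cancellation of a true RR of 0.85 needs s × u = 1/0.85 − 1 = 0.176. With s = 60%, that is u = 0.176/0.60, or about 29%. Of the upward rows, only the most extreme reaches it; the others attenuate.

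**4. What would it do to the test?** Take the 50%/20% row, an overall 10% rise in counted patients. Further assumptions are a 20% true event rate in usual care, 66 providers per arm (about 200/3), 10 to 20 patients each, intra-provider correlation 0.01 to 0.05 and two-sided alpha 0.05.
- With no true effect, the chance of a significant apparent harm is 11% to 21%, against 2.5% in that direction without bias.
- With a true RR of 0.80, the chance of detecting the benefit falls from 35–69% to 15–30%.

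**The case against.** The case on the other side is substantial, and most of it stands as a limit on the point.

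- **Alert content.** A reader might infer that the tool tells providers about falls, sedation and confusion by name. The alert text is not reproduced; Section 5.2 says only that it explains why the drug is dangerous. The link to these outcomes is an inference, supported by the objectives table but not proved by it.
- **Algorithms.** A reader might infer that every office claim counts. The plan does not say so. A validated algorithm may already require inpatient or emergency codes, and where it does the point falls for that outcome. But validation describes overall accuracy; it does not ensure equal sensitivity when one arm is prompted and the other is not.
- **Direction.** A reader might infer that coding will rise in the active arms. Nothing in the documents establishes this. A provider who has stopped the drug may be less inclined to code a drug-related event.
- **Redefining the main outcome.** A stronger remedy would drop randomised providers' claims from the main definition. At s of 40% to 80%, that removes up to the same share of counted patients. It also alters validated algorithms, and it needs a provider-to-claim link the plan does not describe. It would still count other clinicians' codes, including those following the behavioral health referrals the active-arm order set offers. The trade-off does not favour it.
- **Tier.** These outcomes are tertiary, and the plan already includes fractures, hospitalizations and emergency visits as partial checks. That lowers the priority. It does not tell a reader how to interpret a rise confined to coded sedation or falls.

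**Conclusion.** The point holds as a gap in the plan, not as a demonstrated bias. Claims-based falls, sedation, cognitive impairment and other adverse drug events can be coded by unblinded providers who are alerted in the active arms only, and the plan neither restricts the setting nor says how differential capture would be recognised. The direction and amount are unknown. Under the assumed 60% and 20%, a true RR of 0.85 reads about 0.95, which is attenuation, not cancellation. All magnitudes rest on assumed s and u, and those for the test also on an assumed event rate, cluster size and correlation.

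Fractures, all-cause hospitalizations and emergency visits are less exposed. The primary and secondary outcomes come from EHR prescribing data and are unaffected. A reader might infer that the trial's main conclusion is at risk; it is not. What is at risk is the reading of clinical benefit and safety.

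**What to change.** Keep the validated algorithms as the main definition. In Sections 6.2 and 7.3.2, before claims are analysed, add:

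1. For each algorithm, state whether it is already limited to inpatient or emergency codes. Where it is, nothing further is needed for that outcome.
2. For falls, sedation, cognitive impairment and other adverse drug events, pre-specify a companion analysis with the same model, limited to inpatient and emergency claims.
3. Report event counts by care setting and arm.
4. State that a benefit or harm seen only in office-coded events will be interpreted as possibly due to differential coding.

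This needs a care-setting filter on claims the plan already obtains, some analysis time and a few sentences of text; no provider-to-claim link is required. The downside is fewer events and less precision in the restricted version. If s were 60%, it would keep at most 40% of counted patients, and for uncommon events the standard error of the log RR would grow by roughly 1/√0.40, or 1.6 times. That is why it should sit beside the main definition and not replace it. Pre-specification matters because a definition chosen after the results are seen would carry little weight.

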6.3 Adverse events and unanticipated problems

For provider-subjects, the EHR decision support designed for this trial is only meant to highlight information that could be useful in patient management and prescribing. Therefore, we do not anticipate any safety issues to arise with regards to provider-subjects who receive the electronic decision support, and the IRBs who have reviewed our prior proposals have agreed with this general approach.

For patient-subjects, we do not anticipate the occurrence of any adverse events as a result of providers receiving decision support aimed at reducing the use of potentially unsafe medications that already have established clinical guidelines advising against their use. The decision support provides resources to help patients safely discontinue the high-risk medications under study (e.g., providing tapering guidelines and facilitating the substitution of lower-risk therapies). There is a theoretical risk of precipitating withdrawal, but the risk is less than the continued risks of ongoing use of the drugs being addressed by the interventions.

We will ensure the safety of patient-subjects by leaving ultimate clinical decision-making in the hands of the evaluating provider who is in charge of caring for the patient. The study team will not be providing any direct care to patients, and all treatment decisions will ultimately be made by the patients' own medical teams. As a result, any adverse events will be handled in the course of regular clinical care. Further, to maximize the generalizability of the results and to avoid co-intervention, patients will not be required to have study-specific monitoring as part of the proposed pragmatic trials. Therefore, we do not plan to use any patient-directed prospective monitoring of Adverse Events (AEs) or Significant Adverse Events (SAEs) in this trial. An *Adverse Event (AE)* is defined as any untoward or unfavorable medical occurrence in a human study participant, including any abnormal sign (e.g. abnormal physical exam or laboratory finding), symptom, or disease, temporally associated with the participants' involvement in the research, whether or not considered related to participation in the research.

- Adverse Events will be classified using the following rating scales:

- o Severity: Mild, Moderate or Severe

- Mild: Awareness of signs or symptoms but are easily tolerated
- Moderate: Events introduce a low level of inconvenience or concern but may interfere with daily activities but are usually improved by simple therapeutic measures
- Severe: Events interrupt the participants' normal daily activities and generally require systemic drug therapy
- Expectedness: Unexpected or Expected
 - Unexpected: nature or severity of the event is not consistent with the condition under study
 - Expected: event is known to be associated with the intervention or condition under study.

Serious Adverse Event (SAE) are defined as any adverse event that results in death, is life threatening, or places the participant at immediate risk of death from the event as it occurred, requires or prolongs hospitalization, causes persistent or significant disability or incapacity, results in congenital anomalies or birth defects, and is another condition which investigators judge to represent significant hazards.

However, our plan for data and safety monitoring does include multiple mechanisms to ensure minimal risk of participation in the trials. We will leverage an automatic adverse event reporting and review system to observe and monitor for any SAEs that do occur. In specific, providers report adverse events through an online reporting system. Any reports of deaths will be submitted to the NIA Program Officer and to the Data Safety Monitoring Board (DSMB) Chair or designated DSMB member within 24 hours. Any unanticipated SAEs deemed by the specialists and to be related to the intervention will be reported to the NIA PO and to the DSMB Chair or to the designated DSMB member within 48 hours of the study's knowledge of the SAE. All other reported SAEs and AEs received by the study team will be reported to the NIA

Program Officer and to the DSMB quarterly, unless otherwise requested by the DSMB or a Safety Officer.

7. Statistical Considerations

7.1 Statistical Hypotheses

Our null hypothesis will be that rates of provider prescribing (defined by evidence of a reduction in prescribing of high-risk medication) in the intervention arms will be no different than in the other arms, including the usual care arm.

7.2 Sample size determination

We should have >80% power to detect absolute differences of 10% or smaller in the reduction in prescribing between each intervention arms and usual care, assuming an intra-provider correlation of 0.1 (which is based on prior work including the Atrius trial) and a baseline rate of the primary outcome of 25% in the usual care arm. We plan to use Holm-Bonferroni correction to account for multiple testing between each of the intervention arms and usual care, but we will be powered even if using a Bonferroni correction. Our assumptions will also be robust to a slightly higher baseline rate of the primary outcome in the usual care arm. We should also be sufficiently powered to detect meaningful differences in the clinically significant adverse events.

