3.2 Overall design

We will conduct a parallel group trial at Mass General Brigham, specifically within MGH primary care practices. We hypothesize that these tools will reduce prescribing of high-risk medications (primary outcome), cumulative prescribing of high-risk medications (secondary outcome), and clinically-significant adverse drug events like sedation and confusion (tertiary outcome) compared with usual care.

3.2.1 *Trial Design*

[figure not shown]
This trial is a cluster-randomized, NIH-defined Phase III pragmatic trial. The study statistician, in partnership with data analysts at MGB, will generate and implement the randomization scheme, with oversight by the Principal Investigators. All the study sites will be at MGH for this trial; we have received approval from leadership at MGH primary care practices and Digital Health eCare teams to conduct this trial. For study evaluation, data regarding patients' medical history, disease control, medication use, and healthcare utilization will be obtained from EHR data or administrative claims data. Any administrative claims data used for evaluation in this study will come directly from MGB in HIPAA-limited datasets through their risk-bearing contracts.

We will randomize primary care providers at MGH to one of the 2 most promising treatment arms identified in the prior adaptive randomized trial conducted at Atrius Health or usual care (described in further detail in 5.2). We expect to randomize approximately 200 providers. Providers randomized to one of the 2 selected treatment arms will receive an EHR tool to guide their care of eligible patients. We will randomize providers based on provider demographic characteristics, patient case-mix factors, and baseline rates of high-risk medication prescribing measured in EHR data.

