7.3.2 Analysis of secondary endpoints

For the secondary outcome of cumulative medication prescribing, we will use an identity link function and normally distributed errors within the generalized linear models. For tertiary adverse clinical outcomes and resource utilization outcomes, we will use a log link function and binary distributed errors. These models generate the estimated relative risks (RRs) with robust standard errors and are considered to be particularly appropriate when outcomes are common (e.g., incidences of $\geq 10\%$). For these outcomes from claims data, we will follow patients whose providers are randomized to the study from the time of randomization until they are censored due to loss of continuous enrollment in their health plan. Due to the nature of the randomization, we do not anticipate any systematic differences in the amount of follow-up time per arm but will account for any imbalances using inverse probability censoring weights.

Because this is a randomized trial, our primary analyses are planned as unadjusted; however, if there are strong patient-level predictors of the outcomes not balanced by stratified randomization, we will adjust for these. Given the nature of the data and how the outcomes are being measured, there should not be missing values. However, should there be sufficient missing data (e.g., $> 10\%$), we will use multiple imputation.²⁵

7.3.3 *Baseline descriptive analyses*

We will report the means and frequencies of pre-randomization variables separately for intervention and control subjects. Comparisons of these values will be performed using t-tests and chi square tests and their non-parametric analogs, as appropriate. The outcomes will be evaluated using intention-to-treat principles among all randomized patients.

7.3.4 *Subgroup analyses*

In subgroup analyses, we will explore whether there were any modifiers of the effects of the EHR tools. For example, we will explore if certain types of providers (e.g., by specialty) were more likely to respond to the EHR tools or if there were observable differences in patients who were less likely to receive inappropriate medications, such as gender or race/ethnicity.

7.3.5 *Exploratory analyses*

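### Does the unsupported statement of adequate power for adverse events in Section 7.2 call for a change to the plan?

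*Combined protocol and SAP*

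**What the plan says.** Section 7.2 sets out power for the prescribing outcome: more than 80% for "absolute differences of 10% or smaller in the reduction in prescribing", "assuming an intra-provider correlation of 0.1" and "a baseline rate of the primary outcome of 25% in the usual care arm", with a Holm-Bonferroni correction over the two comparisons with usual care. It then adds "We should also be sufficiently powered to detect meaningful differences in the clinically significant adverse events". Section 3.2.1 gives the number of clusters: "We expect to randomize approximately 200 providers".

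The clinical events are defined in Section 6.2 as tertiary outcomes, "including but not limited to, sedation or cognitive impairment, and all-cause hospitalizations and falls or fractures, measured in administrative claims data". On the population, Section 6.2 says "these outcomes will be conducted among the large subgroup of patients funded by Medicare". Section 7.3.2 plans log-link models giving relative risks with robust standard errors. It says of the claims outcomes that "we will follow patients whose providers are randomized to the study from the time of randomization until they are censored", the reason for censoring being loss of continuous health-plan enrolment. The objectives table in Section 2 labels these endpoints tertiary/exploratory.

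**The concern.** Every number in Section 7.2 belongs to the prescribing outcome. The sentence on adverse events borrows the tone of a power calculation without any of its inputs, and the list of events is open-ended. A reader cannot tell which event, which difference or how many patients the author had in mind.

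There is also a reason for doubt. Events are further down the causal chain than prescribing, so a difference in prescribing is diluted before it reaches them. If the only effect to carry forward is 25% versus 35% of patients with a prescribing reduction, the implied difference in events is small. A null result on falls or hospitalisations, read beside a claim of sufficient power, might be taken as evidence of no benefit or no harm. Reducing adverse drug events is part of the overall hypothesis in Section 2, so the point is not idle.

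**Working it through.** **Inputs from the documents.** About 200 providers in three equal arms, so K = 200/3 = 66.7 per arm; 25% versus 35% for prescribing; ICC 0.1 for prescribing. **Assumed.** Two-sided alpha 0.05, 80% power, event rate p, event ICC, claims-linked patients per provider m, and share of risk removed f.

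**1. The plan's own figure (prescribing).** Per arm, n = (1.960 + 0.842)² × (0.25×0.75 + 0.35×0.65) / 0.10² = 7.85 × 0.415 / 0.01 ≈ 326. The effective size per arm is K·m / (1 + (m − 1)·ICC). Setting this equal to n, with x = n/K, gives m = x(1 − ICC)/(1 − x·ICC). Here x = 326/66.7 = 4.89, so m = 4.89 × 0.9 / 0.511 ≈ 9 patients per provider. With alpha 0.025 (Bonferroni) it is about 13. The primary claim is attainable, and it is not in question here. Section 7.2 gives no figure for events, so there is nothing to reproduce.

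**2. What could be detected for events.** The smallest detectable fall d solves (1.960 + 0.842)² × [p(1 − p) + (p − d)(1 − p + d)] / d² = effective n. With m = 30, effective n is 66.7 × 30 = 2,000 at ICC 0 and 2,000/1.29 = 1,550 at ICC 0.01.

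| Event rate | Detectable fall, ICC 0 | Detectable fall, ICC 0.01 |
|---|---|---|
| 50% | 4.4 points | 5.0 points |
| 30% | 4.0 points | 4.5 points |
| 20% | 3.4 points | 3.9 points |
| 10% | 2.5 points | 2.8 points |

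Check at 20%, ICC 0: 7.85 × (0.160 + 0.138) / 0.0342² ≈ 2,000.

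**3. What a 10-point prescribing difference would imply.** Suppose events change only through the prescribing composite, and patients with and without a reduction have the same underlying risk. The active-arm rate is then q = p(1 − 0.35f)/(1 − 0.25f), a relative fall of 0.10f/(1 − 0.25f). This is 0.10/0.75 = 13.3% if a reduction removes all risk (f = 1) and 0.05/0.875 = 5.7% if it halves risk (f = 0.5). Claims-linked patients per provider needed for 80% power:

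| Event rate | All risk removed, ICC 0 | All risk removed, ICC 0.01 | Risk halved, ICC 0 |
|---|---|---|---|
| 50% | 13 | 15 | 72 |
| 30% | 30 | 42 | 165 |
| 20% | 50 | 100 | 282 |
| 10% | 112 | unattainable | 632 |

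The unattainable entry arises because 7,468 effective patients per arm are needed and the ceiling is K/ICC = 66.7/0.01 = 6,667.

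**4. Sensitivity.** If the extra patients whose prescribing is reduced because of the tools carry 1.5 times the others' risk, the relative fall with all risk removed is 0.15/(0.90 + 0.15 − 0.25) = 18.8%. The requirement drops to 7, 15, 25 and 55 patients per provider at ICC 0. At the other end, an event ICC of 0.1 caps the effective size at 66.7/0.1 = 667 per arm and puts 80% power out of reach at all four rates even with all risk removed under equal risk. The plan gives that ICC for prescribing, not for events.

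**5. Comparison with the sentence.** Step 2 addresses what the sentence asserts, namely detection of differences judged meaningful. Step 3 addresses a different matter: whether the trial would detect the event difference implied by one assumed pathway from one prescribing difference. Section 7.2 does not define a meaningful event difference in that way, and its 10 points is a limit of detectability, not a forecast. Section 3.5 also notes that lower doses or alternative drugs may attenuate adverse effects. A binary composite of discontinuation or taper does not capture all of that.

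**The case for a change.** The strongest case for a change is that exploratory outcomes need no power statement, yet this plan makes one. Section 6.3 plans no patient-directed prospective monitoring of adverse events, and Section 6.2 describes EHR capture of clinical outcomes as insensitive. Although Section 6.3 provides for provider reports, the claims comparison is thus the main systematic look at clinical consequences between arms. Under the pathway in step 3, with 30 patients per provider and ICC 0, a doubling of risk after a reduction would raise events by 0.10/1.25 = 8.0% in relative terms. It would be detected with power of only 37, 24 and 13% at event rates of 30, 20 and 10%. Deleting the sentence would cost almost nothing.

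The missing inputs stand: an event rate, target event difference and event ICC appear nowhere in the text, and neither does a patient count, although the design figure and study schema are not visible and might carry one. So does the caution that a non-significant result on these outcomes must not be read as absence of effect. The inference that the claim is probably false does not stand, because its result is set by the assumed inputs. Nor would a rewording raise the power or alter what is estimated. Section 7.3.2 already provides relative risks with robust standard errors, from which confidence intervals follow, and nothing in the plan equates non-significance with no effect. Section 3.7 also says the Medicare data agreements are still being executed, so detectable differences based on claims data may not yet be computable.

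**Conclusion.** The sentence is unsupported and cannot be checked, but it is not shown to be wrong. On assumed inputs it may be true or false. Falls of roughly 2.5 to 5.0 points are detectable with 30 claims-linked patients per provider and an event ICC of 0 to 0.01, while the carry-through from prescribing needs anything from about 7 patients per provider to more than the design can supply. Only the provider count, equal allocation and the 25% and 10-point prescribing figures come from the plan. Event rates, event ICC, patients per provider, share of risk removed and relative risk of the extra patients are all assumptions.

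This is missing detail about tertiary, exploratory outcomes. It does not touch the primary power claim, sample size, alpha allocation, any decision rule or any estimate. Analysts will report relative risks with their uncertainty, and those intervals will show what the data can and cannot exclude better than a planning statement could. No change to the plan follows.
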